5.1.2.1 Other imputations

Incomplete date of initial diagnosis of cGvHD

Missing day is defaulted to the 15th of the month and missing month and day is defaulted to 01-Jan.

5.2 AEs coding/grading

Adverse events are coded using the Medical dictionary for regulatory activities (MedDRA) terminology.

The latest available MedDRA version at the time of the analyses should be used. The MedDRA version used should be specified in the footnote of relevant tables.

AEs will be assessed according to the Common Terminology Criteria for Adverse Events (CTCAE) version 4.03.

The CTCAE represents a comprehensive grading system for reporting the acute and late effects of cancer treatments. CTCAE grading is by definition a 5-point scale generally corresponding to mild, moderate, severe, life threatening, and death. This grading system inherently places a value on the importance of an event, although there is not necessarily proportionality among grades (a grade 2 is not necessarily twice as bad as a grade 1).

5.3 Laboratory parameters derivations

Grade categorization of lab values will be assigned programmatically as per NCI Common Terminology Criteria for Adverse Events (CTCAE) version 4.03. The calculation of CTCAE grades will be based on the observed laboratory values only, clinical assessments will not be taken into account. The criteria to assign CTCAE grades are given in Novartis internal criteria for CTCAE grading of laboratory parameters. The latest available version of the document based on the underlying CTCAE version 4.03 at the time of analysis will be used. For laboratory tests where grades are not defined by CTCAE v4.03, results will be graded by the low/normal/high (or other project-specific ranges, if more suitable) classifications based on laboratory normal ranges.

A severity grade of 0 will be assigned for all non-missing lab values not graded as 1 or higher. CTCAE Grade 5 is not defined for laboratory values. For laboratory tests that are graded for both low and high values, summaries will be done separately and labelled by direction, e.g., sodium will be summarized as hyponatremia and hypernatremia.

Imputation Rules

CTC grading for blood differentials is based on absolute values. However, this data may not be reported as absolute counts but rather as percentage of WBC.

The following rules will be applied to derive the WBC differential counts when only percentages are available for a xxx differential

$$\text{xxx count} = (\text{WBC count}) * (\text{xxx \%value} / 100)$$

CTC grades for the derived absolute WBC differential counts (neutrophils, lymphocytes) will be assigned as described above for grading.

5.4 Statistical models

5.4.1 Primary analysis

Confidence interval for ORR

Responses will be summarized in terms of percentage rates with two-sided 90% confidence interval using exact binomial confidence interval (implemented using SAS procedure FREQ with EXACT statement [Clopper and Pearson 1934]).

5.4.2 Key secondary analysis

Not applicable.

5.4.3 Definition of new or additional systemic treatment of cGvHD

The data source to search for the new or additional systemic therapy would be from eCRFs of “Prior and Concomitant Medication” (CONMED) or eCRFs “Prior or Concomitant non-drug therapies/procedures”.

Systemic therapies are identified using the Route (if CMROUTE is Intramuscular, Intravenous, Oral, Subcutaneous, or Parenteral). Therapies with CMROUTE = ‘ORAL’ will be considered as systemic only if in addition CMADMIN = “SYSTEMIC”.

Any of the following therapies represent new or additional systemic therapy for cGvHD:

- Any CNI therapy being initiated newly as ‘treatment for cGvHD’ or ‘treatment for SR-cGvHD’ after the baseline (as recorded on CONMED). That means when a subject starts a new systemic therapy during study treatment for the indication ‘treatment for cGvHD’ or ‘treatment for SR-cGvHD’, or a subject received the same therapy before as prophylaxis and then changed to treatment of cGvHD/SR-cGvHD as indication, this will be considered as new or additional systemic treatment.

CNI therapy given as ‘treatment for cGvHD’ or ‘treatment for SR-cGvHD’ that started after Cycle 1 Day 1 will be considered as new or additional systemic treatment, even if the same therapy was given as treatment for (SR-) cGvHD already before start of study treatment but the patient was not receiving such therapy on Cycle 1 Day 1. Whereas a stop of such therapy after Cycle 1 Day 1 and later re-start of the same therapy will not be considered as new or additional therapy.

Change of the drug within the defined group of CNIs or only change of the dose is not considered as new CNI treatment.

- Any other systemic treatments (excluding CNI and steroids) being initiated newly as ‘treatment for cGvHD’ or ‘treatment for SR-cGvHD’ after the baseline and documented in CONMED (according to the same definitions as for CNI treatments above).
- Any other non-drug therapy/procedure being initiated newly as ‘treatment for cGvHD’ or ‘treatment for SR-cGvHD’ after the baseline (according to the same definitions as for CNI above) and documented on concomitant non-drug therapies/procedures (e.g. ECP).

Changes in the systemic corticosteroid therapy (captured on study treatment eCRF), e.g. change of the drug, the dose or any interruption and re-start, will not be taken into account for identification of new or additional systemic therapy, nor will any other corticosteroid therapy (in CONMED) be considered.

6 Reference

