In order to summarize data collected over time (including unscheduled visits), the assessments will be time slotted. The following general rule will be applied in creating the assessment windows: If more than one assessment is done within the same time window, the assessment performed closest to the target date will be used. If two assessments within a time window are equidistant from the target date, then the earlier of the two assessments will be used. If multiple assessments on the same date then the worst case will be used. Data from all assessments (scheduled and unscheduled), including multiple assessments, will be listed.

The following time windows are defined for descriptive summary on cGvHD assessment, biomarkers, and safety (Table 2-1) by visit. The end of treatment assessment will be mapped into the time points as needed.

Table 2-1 Time windows for cGvHD assessment and safety assessment (lab, vital sign, etc.)

Time Window	Planned Visit Timing	Time Window Definition
On treatment		
Baseline	On or before Study Day 1	≤ Study Day 1
Cycle 1 Day 8	Study Day 8	Study Days 5 – 11
Cycle 1 Day 15	Study Day 15	Study Days 12 – 18
Cycle 1 Day 22	Study Day 22	Study Days 19 – 25
Cycle 2 Day 1	Study Day 29	Study Days 26 – 39
Cycle 3 Day 1	Study Day 57	Study Days 47 – 67
Cycle 4 Day 1	Study Day 85	Study Days 75 – 95
Cycle 5 Day 1	Study Day 113	Study Days 103 – 123
Cycle 6 Day 1	Study Day 141	Study Days 131 – 151
Cycle 7 Day 1	Study Day 169	Study Days 159 – 179
Cycle 9 Day 1	Study Day 225	Study Days 211 – 239
Cycle 12 Day 1	Study Day 309	Study Days 295 – 323
every 12 weeks	+ 84 day	+84 days to lower and upper bound
Cycle 39 Day 1	Study Day 1065	Study Days 1051 – 1179
Safety follow-up	30 days after last dose	Last dose date + 30
Study Day 1 = start date of study treatment; EOT assessments are mapped to the time points as needed.		

Last contact date

The last contact date will be derived for patients not known to have died at the analysis cut-off using the last complete date among the following:

Table 2-2 Last contact date data sources

Source data	Conditions
Last contact date/last date patient was known to be alive from Survival Follow-up page	Patient status is reported to be alive, lost to follow-up or unknown.
Start/End dates from new cGvHD treatment since discontinuation from study treatment	Non-missing medication/procedure term.
Start/End* dates from drug administration record/concomitant medication record	Non-missing dose. Doses of 0 are allowed.

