Date of discontinuation from end of treatment pages	No condition.
- cGvHD assessment date	Non-missing assessment.

Source data	Conditions
- any specific efficacy assessment date if available (e.g. graft failure assessment, hematologic disease relapse/progression assessment)	
Laboratory/PK collection dates/Biomarker collection dates	Sample collection marked as 'done'.
Vital signs date	At least one non-missing parameter value.
Assessment date of development information (e.g. tanner staging)	Evaluation is marked as 'done'.
Collection date of acceptability and palatability questionnaire	Assessment performed is "Yes".
Start/End dates of AE	Non-missing verbatim term

The last contact date is defined as the latest complete date from the above list on or before the data cut-off date. The cut-off date will not be used for last contact date, unless the patient was seen or contacted on that date. No date post cut-off date will be used. Completely imputed dates (e.g. the analysis cut-off date programmatically imputed to replace the missing end date of a dose administration record) will not be used to derive the last contact date. Partial date imputation is allowed for event (death)/censoring if coming from 'Survival information' eCRF.

The last contact date will be used for censoring of patients in the analysis of overall survival, failure free survival, non-relapse mortality, and malignancy relapse/recurrence.

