2.4.2.4 Additional systemic cGvHD therapy

New additional systemic cGvHD therapy (medications and procedures) since start of study treatment will be listed and summarized by lowest ATC class, preferred term, overall and by Age group by means of frequency counts and percentages using FAS.

Initiation of systemic CNI at the time of or after start of study treatment despite absence of lack of efficacy will be counted as new additional systemic treatment. Note: Although the protocol does not explicitly prohibit initiation of systemic CNI at time of randomization or initiation of study treatment potential impact of CNI on efficacy outcome in responders cannot be excluded.

See Appendix [Section 5.4.3](#) for more detailed specifications.

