2.7.1 Secondary endpoints

Failure Free Survival

FFS is a composite time to event endpoint incorporating the following FFS events: i) relapse or recurrence of underlying disease or death due of underlying disease, ii.) non-relapse mortality, or iii.) addition or initiation of another systemic therapy for cGvHD. If a patient did not experience any of these events, FFS will be censored at the latest contact data (on or before the cut-off date).

Best overall response (BOR)

Analyses of BOR at Cycle 7 Day 1 will not be repeated, whereas BOR up to end of study will be analyzed for the final CSR.

Best overall response (BOR) is defined as proportion of subjects who achieved overall response (CR or PR) at any time point up to and including Cycle 7 Day 1 and before the start of additional systemic therapy for cGvHD.

An additional analysis will include all response assessments up to End of Treatment of the subjects or data cut-off date and before the start of additional systemic therapy for cGvHD. Note,

for subjects who tapered off, all response assessments, including those collected after ruxolitinib discontinuation, will be considered for the analysis.

BOR will be calculated based on the FAS using local investigators' overall response assessments.

ORR at Cycle 4 Day 1 (end of Cycle 3)

Analysis of ORR at Cycle 4 Day 1 will not be repeated for the final CSR.

ORR at Cycle 4 Day 1, defined as the proportion of patients with complete response (CR) or partial response (PR), according to the NIH Consensus Criteria (Lee 2015). ORR will be calculated based on the FAS using local investigators' overall response assessed at the Cycle 4 Day 1 visit and taking into account initiation or addition of new systemic therapy before this time point.

Duration of Response

Duration of response (DOR) is assessed only for responders up to Cycle 7 Day 1 (i.e. all subjects with BOR = CR or PR considering response assessments up to Cycle 7 Day 1). DOR is defined as the time from first response until cGvHD progression, death, or the date of additional systemic therapies for cGvHD. Subjects without event will be censored at the date of their last response assessment prior to or at the analysis cut-off date if no events occurred on or before 12 weeks (84 days) after the last GvHD assessment.

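### SAP 5.4.3 searches too narrowly for new systemic cGvHD therapy as an FFS event: it names two eCRFs and one sentence stops at the last ruxolitinib dose, while Table 2-2 uses a post-discontinuation source for the FFS censoring date

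*SAP*

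**What the plan says.** **Event.** SAP 2.7.1 makes addition or initiation of another systemic therapy for cGvHD the third FFS event, with no time limit. Otherwise, "If a patient did not experience any of these events, FFS will be censored at the latest contact data". SAP 2.7.2 asks for FFS and the cumulative incidence of each component out to 36 months. Table 1-1 marks FFS for inclusion in the final CSR.

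**Search.** SAP 5.4.3 is the only operational definition of such therapy: "The data source to search for the new or additional systemic therapy would be from eCRFs of" prior and concomitant medication (CONMED), or the non-drug therapies and procedures. No other form is named. Corticosteroid changes are excluded.

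**Timing.** The 5.4.3 bullets count therapy newly started post-baseline. The sentence explaining them, however, applies "when a subject starts a new systemic therapy during study treatment for the indication" of treating cGvHD. SAP 2.4.2.4, which refers to 5.4.3 for details, covers "New additional systemic cGvHD therapy (medications and procedures) since start of study treatment". SAP 2.1.1 defines the end of study treatment as the last non-zero ruxolitinib dose.

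**Censoring.** Table 2-2 in SAP 2.1.1 lists "Start/End dates from new cGvHD treatment since discontinuation from study treatment" as one source of the last contact date. A different row holds "Start/End* dates from drug administration record/concomitant medication record". The text then states: "The last contact date will be used for censoring of patients in the analysis of overall survival, failure free survival", along with two other endpoints.

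**The concern.** The same fact, a first start of new cGvHD treatment after ruxolitinib is stopped, has two roles. By the definition in SAP 2.7.1 it is an FFS failure. By Table 2-2 it is evidence of contact, which can move the censoring date later. SAP 5.4.3 does not name that source when it looks for failures. Read literally, its timing sentence also excludes every therapy begun after the last dose.

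At stake are the FFS curve at its landmark times and the split of failures between new therapy, relapse and non-relapse death. Duration of response (DOR) uses the same kind of event, but only where it occurs soon enough after the last assessment: censoring applies "if no events occurred on or before 12 weeks (84 days) after the last GvHD assessment".

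**Working it through.** **1. Sources side by side.**

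| Item | SAP place | Form or source | Time limit |
|---|---|---|---|
| FFS event iii | 2.7.1 | not stated | none |
| Event search | 5.4.3 | CONMED; procedures eCRF | bullets: post-baseline; one sentence: study treatment only |
| Summary of new therapy | 2.4.2.4 | refers to 5.4.3 | from start of study treatment |
| FFS censoring date | Table 2-2 | includes new cGvHD treatment after discontinuation, in its own row | data cut-off |

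The two Table 2-2 rows carry different conditions: a non-missing medication or procedure term for the post-discontinuation row, and a non-missing dose for the concomitant medication row. The second and third bullets of 5.4.3 adopt the CNI definitions, so the timing sentence reaches them too.

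**2. Who could be missed.** Protocol 6.1.5 has subjects without benefit stop ruxolitinib and be treated per local practice. SAP 1.1 follows early discontinuers every 6 months to 3 years from first dose. In protocol Table 8-1 the medication and non-drug therapy rows are marked through the 30-day safety visit and blank at early discontinuation follow-up, where height and weight are marked. Protocol 9.1.1 does not list cGvHD therapy among the follow-up assessments. The exposed group is therefore early discontinuers who first start a non-steroid systemic cGvHD therapy more than 30 days after the last dose, recorded only in the Table 2-2 source.

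**3. Size per missed subject.** The documents give no figure to reproduce. Protocol Amendment 2 gives 46 enrolled. Assumptions: 9 captured FFS events in months 0.5 to 12, other losses spread over months 8 to 29, and one missed therapy start.

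No losses, no later event:
- true 36-month FFS = (46 − 10)/46 = 78.26%
- under 5.4.3 as written = (46 − 9)/46 = 80.43%
- difference = 1/46 = 2.17 points

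Kaplan-Meier difference in 36-month FFS, SAP rule minus truth, in percentage points:

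| Others lost | Therapy month 6 | Month 12 | Month 18 | Month 24 | Therapy month 6, death month 30 |
|---|---|---|---|---|---|
| 0 | +2.17 | +2.17 | +2.17 | +2.17 | 0.00 |
| 5 | +2.18 | +2.23 | +2.29 | +2.43 | −0.33 |
| 9 | +2.18 | +2.29 | +2.43 | +2.67 | −0.68 |
| 14 | +2.18 | +2.36 | +2.67 | +2.97 | −1.30 |

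Without a later event, the cumulative incidence of new therapy is too low by the same amounts.

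The last column is negative because the failure is counted late, when fewer subjects are at risk. With 5 lost, 46 − 9 − 5 = 32 are at risk at month 30. The SAP rule gives 80.27% × 31/32 = 77.76%, against a true 78.09%. In that column 12- and 24-month FFS are still 2.17 to 2.18 points too high, and the new-therapy component is too low by the same amount.

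**4. Sensitivity.** With 45 analysed, the ranges are +2.22 to +3.06 without a later event and 0.00 to −1.39 with death at month 30. With 46 analysed, therapy at month 6, and 0, 5 or 15 captured events, they are +2.17 to +2.19 and 0.00 to −1.74.

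**The case against.** The strongest objection is that the eCRF is not in the documents, so the Table 2-2 row may simply filter the two forms already searched. It names no page, unlike neighbouring rows, and its medication-or-procedure condition matches those two forms. This stands: the gap in sources is conditional.

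Three further points narrow it. SAP 2.4.2.5 expects some concomitant therapies that start after the on-treatment period, so CONMED is not shown to close at 30 days. Not every row of protocol Table 8-1 could be read, so a blank cell does not prove non-collection. Protocol 6.2.2 requires ruxolitinib to stop when new systemic immunosuppression is added; therapy that itself triggers stopping should already be in CONMED. Responders who taper off stay on the full visit schedule.

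It can also be said that the timing phrase occurs once and the bullets outweigh it. That does not remove the contradiction, because the sentence states what the bullet means and the other bullets adopt it.

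On size, FFS is secondary and estimated without a test. A rough 95% half-width, 1.96 × √(p(1 − p)/46), is 13.8 points at p = 0.65 and 11.6 at p = 0.80. One subject lies well inside that. This limits the consequence but does not settle which records count as events.

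**Conclusion.** The timing wording in SAP 5.4.3 conflicts with its own bullets, with 2.4.2.4 and with the unlimited FFS event, whatever the eCRF structure. The missing source is a real gap only if the Table 2-2 row is a separate form. SAP 2.7.1 does not cite 5.4.3; the link is that 5.4.3 is the SAP's only definition of the therapy and 2.4.2.4 points to it.

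Under the stated assumptions, each missed subject without a later event raises 36-month FFS by about 2.2 points, up to 3.0 with late therapy and heavy loss, and lowers the new-therapy component equally. The number of such subjects is unknown and may be zero.

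A reader might infer three stronger things, and the documents support none of them:
- **That FFS is materially inflated.** That needs several missed subjects, and nothing shows there is even one.
- **That the bias always favours the drug.** A later relapse or death can leave 36-month FFS unchanged or slightly lower; what stays wrong is the timing and the component.
- **That the primary ORR is compromised.** It is little affected. Protocol 6.5.1.2 counts subjects who meet the discontinuation criteria before Cycle 7 Day 1 as non-responders, and SAP 2.5.3 does the same for a missing assessment.

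DOR can change only if the therapy starts within 84 days after the last cGvHD assessment.

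**What to change.** In SAP 5.4.3:

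1. Replace the limit to the study treatment period with wording that matches 2.4.2.4 and the bullets: from start of study treatment to end of study, including after ruxolitinib discontinuation. Keep a CNI started on Day 1 as an event. Wording that counts only starts after Cycle 1 Day 1 would conflict with 2.4.2.4, which counts a CNI begun at the start of study treatment.
2. Add the post-discontinuation cGvHD treatment source, both medications and procedures, to the event search for FFS, and for DOR within the 84-day rule. If it is only a filter on the CONMED and procedures eCRFs, say so; then only change 1 is needed.

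A cross-reference from the FFS definition in 2.7.1 to 5.4.3 would make the link explicit.

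The cost is small, since the SAP already reads this source for the last contact date. How complete it is after the 30-day visit cannot be judged from the documents. Final FFS may be slightly less favourable. SAP 2.14 uses one SAP for both reports, so any difference from the interim CSR derivation should be noted in the final CSR.

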5.1 Inclusion criteria

Subjects eligible for inclusion in this study must meet **all** of the following criteria:

1. Male or female subjects age ≥ 28 days and < 18 years at the time of informed consent.
2. Subjects who have undergone a successful alloSCT from any donor source (matched unrelated donor, sibling, haplo-identical) using bone marrow, peripheral blood stem cells, or cord blood. Recipients of myeloablative or reduced intensity conditioning are eligible.
3. Subjects with diagnosed moderate to severe cGvHD according to NIH 2014 Consensus Criteria ([Section 16.2](#)) prior to Cycle 1 Day 1. Other possible diagnoses for clinical symptoms supporting the cGvHD diagnosis must be excluded (e.g. infection, drug side effects, malignancy). Subjects must be either:
 - Treatment-naïve cGvHD subjects that have not received any prior systemic treatment for cGvHD except for a maximum 72h of prior systemic corticosteroid therapy of methylprednisolone or equivalent after the onset of chronic GvHD. Subjects are allowed to have received prior systemic treatment for cGvHD prophylaxis (as long as the prophylaxis was started prior to the diagnosis of cGvHD).

OR

- Steroid-refractory moderate to severe cGvHD as per institutional criteria, or per physician decision in case institutional criteria are not available, and still receiving systemic corticosteroids for the treatment of cGvHD for a duration of < 18 months prior to Cycle 1 Day 1; in case the corticosteroids were previously interrupted due to response, the duration of < 18 months applies to the last period of corticosteroids use.

4. Able to swallow study medication or administer the ruxolitinib pediatric formulation by nasogastric (NG) tube, as applicable.
5. Written study informed consent (and assent if appropriate) from the subject and/or parent/legal guardian

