6.1.1 Investigational and control drugs

Table 6-1 Dose and treatment schedule

Investigational treatment	Age groups	Pharmaceutical form and Route of Administration	Dose	Frequency and/or Regimen
Ruxolitinib (INC424)	Group 1 ≥ 12 years old to < 18 years old	5 mg tablet* for oral use OR oral pediatric formulation	10 mg BID (2 tablets orally BID) OR 10 mg BID oral pediatric formulation**	Twice per day
Ruxolitinib (INC424)	Group 2 ≥ 6 years old to < 12 years old	5 mg tablet* for oral use OR oral pediatric formulation*	5 mg BID (1 tablet orally BID) OR 5 mg BID oral pediatric formulation**	Twice per day

Investigational treatment	Age groups	Pharmaceutical form and Route of Administration	Dose	Frequency and/or Regimen
Ruxolitinib (INC424)	Group 3 ≥ 2 years old to < 6 years old	5 mg tablet* for oral use OR oral pediatric formulation	4 mg/m ² BID (either tablet orally OR oral pediatric formulation)**	Twice per day
Ruxolitinib (INC424)	Group 4 ≥ 28 days to < 2 years old	oral pediatric formulation	X mg/m ² BID (oral pediatric formulation)** To be defined from study CINC424F12201	Twice per day

*A whole tablet for oral use may be crushed as per instructions in the pharmacy manual (if calculated dose based on BSA is not 5 mg or 10 mg, then crushing is not permitted. Tablet cannot be broken to achieve partial doses. In this case, oral pediatric formulation should be administered). Oral pediatric formulation should be dispensed according to instructions in the pharmacy manual.
Note: Crushed tablet(s) can only be administered orally and cannot be administered by nasogastric (NG) tube.
**Calculated doses should be rounded to the nearest available volume as per instructions in the pharmacy manual

The Investigator will instruct the subject to take the investigational treatment as per protocol.

All dosages prescribed and dispensed to the subject and all dose changes during the study must be recorded on the Dosage Administration Record electronic case report form (CRF).

Ruxolitinib will be administered orally twice per day at the assigned dose based on age group, given as 5 mg tablets or equivalent dose as oral pediatric formulation.

Ruxolitinib (tablet or oral pediatric formulation) should be taken approximately 12 hours apart (morning and night) without regards to food. Ruxolitinib will be administered by Investigator or delegate, or self-administered by the subject or parent/legal guardian in an outpatient setting.

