2.5.1 Primary endpoint

The primary efficacy variable of the study is **overall response rate (ORR)** at Cycle 7 Day 1, defined as the proportion of subjects demonstrating a complete response (CR) or partial response (PR), according to the NIH Consensus Criteria ([Lee et al 2015](#)) as reported in the CRF. Note that response is relative to the assessment of cGvHD at baseline.

- **Complete response** is defined as complete resolution of all signs and symptoms of cGvHD in all evaluable organs without initiation of any new systemic therapy.
- **Partial response** is defined as an improvement in at least one organ (e.g. improvement of 1 or more points on a 4 to 7 point scale, or an improvement of 2 or more points on a 10 to 12 point scale) without progression in other organs or sites, or initiation/ addition of new systemic therapies.
- **Lack of response** is defined as unchanged, mixed response, or progression. (Please refer to Table 8-3 and Table 16-3 in the protocol for the definitions of "unchanged", "mixed response" and "progression".)

cGvHD Flare and **cGvHD Recurrence** are not considered as a treatment failure, unless they require a change or addition of another systemic treatment defined as below.

- **cGvHD Flare** is defined as any increase in symptoms or therapy for cGvHD after an initial response (CR or PR). A cGvHD flare is not considered a treatment failure unless a change or addition of another systemic treatment, including CNIs, occurs.
- **cGvHD Recurrence** is defined as the return of cGvHD disease after tapering off study treatment due to response. Following completion of a taper of systemic therapy, if worsening of cGvHD symptoms occur, the patient is allowed to resume treatment for cGvHD as per local institutional practice. For the statistical analyses, re-start of treatment for cGvHD is handled in the same way as addition or initiation of new systemic treatment.

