2.5.3 Handling of missing values/censoring/discontinuations

Patients with missing assessments that prevent the evaluation of the primary endpoint will be considered non-responders. This includes missing overall cGvHD response assessments at baseline and/or Cycle 7 Day 1. The time window for the Cycle 7 Day 1 visit is defined in [Table 2-1](#) above.

No data imputation will be applied. Patients who discontinue study treatment should return for the regular assessments indicated in Protocol Section 9.1. Addition or initiation of a new systemic therapy before Cycle 7 Day 1 will be considered a treatment failure, and patients will be counted as non-responder in the primary analysis.

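### The SAP's route list for detecting new systemic cGvHD therapy has no enteral-tube route, so a tube-coded drug would be missed, mainly as an FFS or DOR event

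*SAP*

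**What the plan says.** SAP 5.4.3 is the working rule for finding new or additional systemic treatment of cGvHD. It searches the concomitant-medication and non-drug-procedure forms. A medication is systemic "if CMROUTE is Intramuscular, Intravenous, Oral, Subcutaneous, or Parenteral". Oral records "will be considered as systemic only if in addition CMADMIN" is SYSTEMIC. A record that passes must also be newly started after baseline with cGvHD or SR-cGvHD treatment as its indication. Corticosteroids are left out by design.

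SAP 2.4.2.4 sends the reader to this appendix "for more detailed specifications", and neither document gives another operational definition. For the primary endpoint, SAP 2.5.3 states: "Addition or initiation of a new systemic therapy before Cycle 7 Day 1 will be considered a treatment failure".

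On routes, protocol inclusion criterion 4 requires a subject to be "Able to swallow study medication or administer the ruxolitinib pediatric formulation by nasogastric (NG) tube, as applicable". The note to protocol Table 6-1 keeps the two routes apart: "Crushed tablet(s) can only be administered orally and cannot be administered by nasogastric (NG) tube".

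**The concern.** A five-value list with no catch-all works only if every systemic drug record carries one of the five values. Tube dosing is foreseeable here: the protocol permits it for the study drug and names it as something other than oral. Parenteral does not cover it, since an enteral tube is by definition not parenteral. By the amendment histories, nasogastric dosing entered with protocol Amendment 1, and the detailed therapy-identification rule was added to the SAP later (November 2022) without it.

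A missed record errs in one direction. In FFS and DOR, starting a new systemic therapy is itself an event, so the subject is carried forward as event-free. In the response endpoints, a subject who should be a failure can stay a responder.

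**Working it through.** **Step 1. Run a record through the rule.** Take a non-steroid drug started after baseline, with indication treatment for cGvHD, given by tube.

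- Site records ORAL with CMADMIN = SYSTEMIC: caught.
- Site records a nasogastric, gastrostomy or other enteral code: fails the list whatever CMADMIN says, and is missed.

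The gap therefore exists only if the eCRF offers separate tube codes and sites use them. It concerns drugs; procedures such as ECP come from a different form and have no such route.

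**Step 2. Which endpoints use the rule, and which are in the final CSR (SAP Table 1-1, 2.5, 2.7.1, 2.13).**

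| Endpoint | Role of new systemic therapy | In final CSR |
|---|---|---|
| FFS | is an event | yes |
| DOR | is an event | yes |
| BOR to study end | later responses do not count | yes |
| Corticosteroid-free response | makes a non-responder | yes |
| ORR at Cycle 7 Day 1 | makes a non-responder | only if data changed |
| ORR at Cycle 4 Day 1, BOR to Cycle 7 Day 1 | non-responder / later responses do not count | not repeated |

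**Step 3. Reproduce the plan's figure.** Inputs: n=42, true ORR 0.70, two-sided 90% Clopper-Pearson limits (SAP section 3). Lower limit = 0.05 quantile of Beta(x, n−x+1); upper limit = 0.95 quantile of Beta(x+1, n−x). The smallest x with a lower limit of at least 0.50 is 27, with limits 0.5045 and 0.7653. P(X ≥ 27) for Binomial(42, 0.70) is 0.8360. The SAP prints 0.836 and 0.505 to 0.765. The n=46 row also reproduces: 30 responders, probability 0.809, limits 0.5208 and 0.7682.

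**Step 4. Size of one missed record.** The documents give no count of tube-dosed subjects, so I take 0 to 3 as an assumed range. The protocol reports 46 enrolled; the FAS may be smaller, because the SAP excludes subjects with two named deviations.

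- ORR shift = k/n. At n=46: 1/46 = 2.2, 2/46 = 4.3, 3/46 = 6.5 points. At n=42: 2.4, 4.8, 7.1 points.
- At the threshold count, n=46: 30 to 29 responders moves ORR from 65.2% to 63.0% and the lower limit from 0.5208 to 0.4987. At n=42: 27 to 26 moves the lower limit from 0.5045 to 0.4805. These are the most sensitive points; at other counts the shift is the same but need not cross 50%.
- FFS: without censoring, the Kaplan-Meier estimate at a given time is (number event-free)/n, so one missed event adds 1/46 = 2.2 points from that time until the subject's next recognised event. Earlier censoring makes each event weigh more.
- DOR: the denominator is responders. With 30 responders, for illustration only, one missed event adds 1/30 = 3.3 points.

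**The case against.** The strongest objection is that the CMROUTE code list and eCRF completion guide are not in the documents. If sites enter tube dosing as oral and systemic, nothing is lost. The Table 6-1 note concerns crushed ruxolitinib tablets, not the coding of concomitant drugs. This stands, and it makes the point conditional.

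A reader might infer that the protocol enrols tube-fed children whose other drugs go down the same tube, and that ORR at Cycle 7 Day 1 is therefore inflated. The documents do not support that. Criterion 4 speaks only of the ruxolitinib pediatric formulation. Fourteen subjects were already enrolled when Amendment 1 introduced nasogastric dosing, and 39 of the 46 (22 + 17) were aged 6 or over.

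Several provisions also guard ORR. Protocol 6.2.2 requires ruxolitinib to stop if a new systemic immunosuppressant is added. The early-discontinuation assessments in protocol 9.1.1 include no cGvHD assessment, and SAP 2.5.3 counts a missing Cycle 7 Day 1 assessment as non-response. Response is taken "as reported in the CRF", and the CR and PR definitions exclude new systemic therapy. A sensitivity analysis in SAP 2.5.4 drops subjects given prohibited medication.

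These guards are partial. SAP 2.1.1 lets an end-of-treatment assessment be mapped into Study Days 159 to 179. Protocol 6.5.1.2, under which meeting a discontinuation criterion before Cycle 7 Day 1 means non-response, is not carried into SAP 2.5.3. None of them restores a missed FFS or DOR event.

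Finally, the protocol asks investigators to record any new systemic therapy, and SAP Table 2-2 lists a source for new cGvHD treatment after discontinuation. SAP 5.4.3 does not name that source, so it offers a cross-check but does not close the gap.

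**Conclusion.** The omission is real on the text, and neither document closes it. Its consequence depends on one assumption that cannot be checked here: that tube routes are separate CMROUTE values. If so, a tube-given new cGvHD drug is a missed FFS or DOR event and may leave a false response in BOR to study end or corticosteroid-free response. All four are in the final CSR.

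For ORR at Cycle 7 Day 1 the effect is possible but limited, at about 2.2 points per subject at n=46. The fall of the lower limit below 50% at 29 of 46 should not be read as a changed conclusion: the trial tests no hypothesis, and that count is the most sensitive one. This is a minor specification gap that could favour the drug, not evidence that any reported result is wrong.

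**What to change.** In SAP 5.4.3, add nasogastric, gastrostomy/jejunostomy and other enteral routes, subject to the same CMADMIN = SYSTEMIC check as oral.

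Before final lock, list every post-baseline concomitant-medication record indicated as treatment for cGvHD or SR-cGvHD that the route filter excludes, and have a clinician review it. The source for new cGvHD treatment after discontinuation in SAP Table 2-2 can serve as a cross-check. An empty list documents that the gap had no effect.

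Re-run the interim ORR and BOR only if the listing finds a case before Cycle 7 Day 1. State this explicitly, because SAP 2.5 reopens the primary analysis only when data change, and this would be a change of derivation.

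The cost is one line in the SAP and one listing. No design figure or sample size changes.
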